## SYNOPSIS

Title	Follow-up of the first in man, prospective, open-label, single arm, multicenter clinical investigation to assess the long-term safety and performance of the ARGOS-SC suprachoroidal pressure sensor system in patients with glaucoma underwent non-penetrating glaucoma surgery (Follow-up Month 12 – Month 36)
Study Number	ARGOS-SC01_Follow-up
Sponsor	Implantata Ophthalmic Products GmbH
Name of IMD	
ARGOS-SC System
 
The ARGOS-SC system is a non-CE marked investigational medical device composed of the implant and its accessories:
 
Implant: ARGOS-SC pressure sensor implant for suprachoroidal placement
 
Accessories: MESOGRAPH reading device, telemetric Multiline Connector

Intended use	The sensor device is intended to be permanently implanted in the human eye and used in conjunction with the hand-held MESOGRAPH reading device to telemetrically measure the intraocular pressure (IOP) of the implanted eye.
Patient Population	Subjects of the ARGOS-SC01 clinical trial with an implanted ARGOS-SC pressure sensor.
Study Purpose	The purpose of this study is to evaluate the long-term safety and performance of the ARGOS-SC system.
Study Design	This study is designed as a prospective, open-label, multicenter, single-arm clinical investigation. Subjects will be followed up at regular intervals for 2 years (Month 12 – Month 36) after the ARGOS-SC implantation to collect safety and performance information.
Study Objectives	
Primary Objective
 
Performance
 
To evaluate the limits of agreement between measurements with Goldmann Applanation Tonometry (GAT), Pascal Dynamic Contour Tonometry (DCT, if available) and the ARGOS-SC system from month 12 throughout month 36 following implantation

 Implantata Ophthalmic Products GmbH	Clinical Investigation Plan ARGOS-SC01_Follow-up	Revision C  Page 7 of 97
--	---	--------------------------------

	
Secondary Objectives
 
Safety
 
To evaluate the safety and tolerability the ARGOS-SC pressure sensor throughout a follow-up period from month 12 throughout month 36.
 
Performance
 
To evaluate the performance of the ARGOS-SC system from month 12 throughout month 36 after implantation.

--	---

Study Procedures	
V09 (Month 12/Day 365)
 
is the last Visit of ARGOS-SC01 and the Baseline Visit of ARGOS-SC01_Follow-up
 
Semiannual Follow-up Month 13 (V10) – Month 36 (V13)
 
The examinations performed for each visit are listed without mentioning the single visit in parentheses. The follow-up visits will include:
 
General
 
 
• ADE/SAE/SADE
 
• Device Deficiency
 
• Concomitant Medication
 
• Visual acuity (ETDRS) (OU)
 
• Perimetry (OU)
 
• External eye photography
 
• Heidelberg Engineering ANTERION® (location of ARGOS-SC), if available
 
• National Eye Institute Questionnaire – VFQ-25 (V11, V13)
 
 
Anterior segment (OU)
 
 
• Optical coherence tomography (OCT) of cornea and anterior chamber
 
• Slit lamp biomicroscopy
 
• Gonioscopy
 
 
Posterior segment (OU)
 
 
• Funduscopy
 
• Optical coherence tomography (OCT) of macula and optic nerve
 
• Fundus photography (V11, V13)
 

-------------------------	---

 Implantata Ophthalmic Products GmbH	Clinical Investigation Plan ARGOS-SC01_Follow-up	Revision C  Page 8 of 97
--	---	--------------------------------

	
IOP measurements
 
 
• Goldmann Applanation tonometry (GAT) (OU)
 
• Pascal Dynamic Contour Tonometry (DCT) (if available) (OU)
 
• ARGOS-SC measurements
 
• ARGOS-SC self-measurements
 

Data Analysis and Statistics	
Primary Endpoint
 
Performance
 
 
- Level of Agreement between measurements made using GAT, Pascal DCT and the ARGOS-SC system from V09 (month 12) through V13 (month 36).
 
 
Secondary Endpoints
 
Safety
 
 
- Number of patients experiencing a device-related SAE (SADE) from V09 (month 12) to V13 (month 36)
 
- Incidence, nature, severity and seriousness of observed adverse events and adverse device events at any time from month 12 (V09) through month 36 (V13).
 
 
Performance
 
 
- Repeatability of the ARGOS-SC measurement
 
- Incidence, nature and seriousness of observed device malfunctions from month 12 (V09) throughout month 36 (V13) months follow-up period.
 
 
Utility
 
 
- User acceptance of the ARGOS-SC system at the investigational site by means of evaluation of physician acceptance questionnaires (by investigators)
 
- User acceptance of the ARGOS-SC system at home by means of evaluation of patient acceptance questionnaires (patients)
 
- Daily IOP self-measurement profiles (patients)
 

 Implantata Ophthalmic Products GmbH	Clinical Investigation Plan ARGOS-SC01_Follow-up	Revision C  Page 9 of 97
--	---	--------------------------------

	
Statistical analysis
 
Safety analysis
 
AEs, SAEs, ADEs and SADEs will be listed and analyzed by descriptive and explorative statistical methods.
 
Performance analysis
 
The probability distribution of the difference of the paired measurements grouped within 1 mmHg will be compared to the primary objective of the accepted 65% of the measurements to agree between +/- 5 mmHg for > 60 measurements pairs.
 
Follow-up Analysis
 
A safety and performance summary will be provided after V10, V11, V12 and V13 when all included patients have undergone the appropriate visit.

Data Collection	Data will be collected using a Case Report Form (CRF).
Study Duration	The overall study duration for each individual subject is up to 24 months.

 In the unprobeable case this number of measurement pairs is not reached, the primary objective is to be adjusted according to the actual number of measurement pairs.

 Implantata Ophthalmic Products GmbH	Clinical Investigation Plan ARGOS-SC01_Follow-up	Revision C  Page 10 of 97
--	---	---------------------------------

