The greatest limitation however is, because a slit-lamp based, GAT readings have to be performed in a clinic or office setting with the patient in a seated position, limiting the frequency and ease with which readings can be made [7].

 IOP Implantdata Ophthalmic Products GmbH	Clinical Investigation Plan ARGOS-SC01_Follow-up	Revision C  Page 20 of 97
---	---	---------------------------------

*Pascal Dynamic Contour Tonometry*

In Pascal Dynamic Contour Tonometry (DCT), IOP is measured by determining the force required to mould the cornea to the shape of the concave probe [8]. While it is far less influenced by corneal parameters than GAT, this method is still dependent on the assumption that the corneal properties, including rigidity, curvature and elasticity are within the normal range. As with GAT, the use of a slit-lamp is required, necessitating a clinic visit and limiting the frequency and ease with which it can be used. Direct corneal contact is also required, with its associated need for anaesthesia and risk of corneal damage and infection.

The accuracy of all devices that use secondary dimensions to estimate IOP is limited to the degree that the secondary biometric parameters they measure, principally the force needed to applanate a section of the cornea or sclera, are affected by factors other than IOP, such as corneal thickness [12]. The majority of contact tonometers require use of corneal anaesthetics. The greatest limitation however is that almost all of the devices are cumbersome and require skill and training to use, in effect limiting their use to the clinic /office setting.

The cost and inconvenience of the required office visits result in treatment decisions that are made based on only a few IOP measurements taken months apart. However, fluctuations in IOP due to patient activity and circadian rhythm are normal. The level of imprecision in repeated IOP measurements has been estimated at +/- 5 mmHg, meaning that to be 95% certain there is any treatment effect, a difference greater than 7 mmHg must be seen between single pre- and post-treatment IOP levels [13]. When 24-hour IOP profiles are taken, which require patients be admitted to the clinic, peak values – thought to be the most relevant for patient outcome in the long term – are seen outside of normal office hours in 80% of the cases, resulting in changes to treatment [2, 14].

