### **8.3.6      Number of subjects required**

This exploratory investigation will enroll maximal 24 patients.

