### **8.3.11     Performance**

IOP level will be assessed at every follow-up visit in a series of 2 GAT standard measurements followed by 3 consecutive measurements with the ARGOS-SC system and if available, additional 2 DCT measurements followed by 3 consecutive measurements with the ARGOS-SC system.

Patients were given a MESOGRAPH reading device at Visit 01 in order to measure the IOP daily at home. Measurements shall be taken at least 4 times per day (morning, noon, afternoon, evening). The

 IOP Implantata Ophthalmic Products GmbH	Clinical Investigation Plan ARGOS-SC01_Follow-up	Revision C  Page 59 of 97
---	---	---------------------------------

MESOGRAPH reading device will be connected to an external GSM module, which will transfer the measured value directly to a secure database. Investigators can log into the database in order to track the pressure levels of their patients as required. At every follow-up visit, site staff will examine the subject's hand-held reader device and download all readings recorded since the last visit. In addition, they will ask subjects non-leading questions to determine if any device deficiencies occurred since the last visit. All device deficiencies will be recorded on the device deficiency page of the CRF. To ensure accuracy and comparability of the recorded parameters, all responsible site personnel will be thoroughly instructed on the agreed measurement methods.

To access the user acceptance of the general usability of the ARGOS-SC system, physicians and personnel performing the ARGOS-SC system measurements will be asked to complete user acceptance questionnaires. The aim of these questionnaires is to gain more information about the level of user-acceptance of the ARGOS-SC system during IOP measurement. The data collected with these questionnaires is only of exploratory nature and will not be included in the analysis. Results will provide the sponsor with data that could influence future device system improvements.

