#### **9.1.4 Performance Analysis**

The probability distribution of the difference of the paired measurements grouped within 1 mmHg will be compared to the primary objective of the accepted 65% of the measurements to agree between +/- 5 mmHg for > 60 measurement pairs.

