#### **9.2 Sample Size Calculation**

Given by the exploratory nature of this study, the sample size is not driven by the need for a formal statistical hypothesis test with a certain degree of power. Instead, this study is driven by the desire to obtain a clinically meaningful amount of data to evaluate the long-term safety and performance of the ARGOS-SC system in patients who have been already implanted with the study device. Therefore the maximum sample size is 24. The minimal sample size for this study is at the Sponsor's direction. This is considered to be appropriate since no experimental treatments are planned and all assessments with exception of IOP measurement using the ARGOS-SC device are established standard methods.

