#### **9.5 Criteria for termination of the clinical investigation**

The participation of an individual site in the study will be discontinued if the sponsor, the investigator or the responsible ethics committee deems it necessary for any reason.

The complete study will be discontinued:

- If the sponsor and/or any responsible regulatory authority or ethic committee judges it necessary for any reason. See also Section 8.3.2 Discontinuation or Withdrawal Criteria Early Patient Withdrawal and Section 11.11 Criteria for Suspension and Premature Termination of Study

---

 In the unprobeable case this number of measurement pairs is not reached, the primary objective is to be adjusted according to the actual number of measurement pairs.

 IOP Implantata Ophthalmic Products GmbH	Clinical Investigation Plan ARGOS-SC01_Follow-up	Revision C  Page 71 of 97
---	---	---------------------------------

- If, throughout the course of the study, the DSMB comes to the conclusion that the ARGOS-SC pressure sensor would expose the subject study patients to undue risk

All patients will continue to be followed up. If the study is discontinued for safety reasons it will be proven whether explantation of all ARGOS-SC sensors deems necessary or follow-up of patients is sufficient.

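### If 60 or fewer measurement pairs are obtained, the protocol lets the primary objective be adjusted without a rule, in an open-label study, and the SAP drops the criterion without saying so

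*Protocol*

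**What the plan says.** Protocol section 9.1.4, like the Synopsis, has the distribution of paired differences "compared to the primary objective of the accepted 65% of the measurements to agree between +/- 5 mmHg for > 60 measurement pairs". A footnote at both places calls a shortfall improbable and says that if "this number of measurement pairs is not reached, the primary objective is to be adjusted according to the actual number of measurement pairs".

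The provisions that determine the pair count are:

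- **Enrolment.** Protocol section 8.3.6: "This exploratory investigation will enroll maximal 24 patients". Section 9.2: "The minimal sample size for this study is at the Sponsor's direction". Section 5 expects that some ARGOS-SC01 patients will not continue.
- **Visits.** Section 8.2.1 compares values from five visits, V09 to V13.
- **DCT.** It is part of the primary endpoint (section 8.1.3.1) but is optional. Section 8.3.11 provides, after the GAT series, "if available, additional 2 DCT measurements followed by 3 consecutive measurements with the ARGOS-SC system".
- **Unit.** The protocol does not define a measurement pair. SAP section 8.5.1 averages the readings of each method at each visit and treats DCT in the same way as GAT.

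SAP section 8.5.1 splits the absolute difference at 5 mmHg, and the Table 2.1.1 mock-up shows this by visit. The 65%, the count of more than 60 and the adjustment do not appear in the SAP. Section 9 of the SAP lists two changes from the protocol, on self-measurements and interim analyses, and neither concerns this criterion.

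**The concern.** An acceptance criterion informs only if it is fixed before the results can be seen. Here the protocol directs that the primary objective itself be changed once the number of pairs is known. Section 11.12 confirms that nothing is masked, so whoever makes the change may already know the share within 5 mmHg. The text does not say whether the 65% goes up, goes down or is set aside, by how much, when, or by whom.

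The usual safeguards would not catch this. Protocol section 9.6 requires significant deviations from the statistical plan to be reported. An adjustment that the protocol itself directs, to a criterion that the SAP does not contain, would be a deviation from neither document. A reader of the final report could not tell a planned criterion from one chosen to fit the data.

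**Working it through.** **1. Can the adjustment be inferred from how the figures were set?** No derivation is given for 65% or for more than 60. Protocol section 9.3 states a significance level of 0.10 and 80% power but no hypotheses, while section 9.2 says no formal test drives the sample size. The one-sample formula is

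n = [(z_alpha √(p0(1−p0)) + z_0.80 √(p1(1−p1))) / (p1−p0)]²

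| Assumed p0 vs p1 | one-sided | two-sided |
|---|---|---|
| 50% vs 65% | 48.3 | 66.6 |
| 65% vs 80% | 39.9 | 55.9 |

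Neither assumed pair reproduces 60. The hypotheses are assumptions, so this does not show that 60 is wrong. It shows only that the documents give no formula from which an adjusted bar would follow.

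**2. GAT pairs, one averaged pair per patient-visit (SAP section 8.5.1).**

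- Maximum: 24 × 5 = 120.
- 12 patients with all visits: 12 × 5 = 60, which is not more than 60.
- 13 patients with all visits: 13 × 5 = 65. So at least 13 complete patients are needed, or more patients if visits are missed.

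**3. DCT pairs, if the count applies to each comparator.** Share of patient-visits that must include DCT = 61 / (patients × 5 × attendance). The patient numbers below 24 and the attendance rates are assumptions.

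| Patients | Attendance | Patient-visits | DCT share needed |
|---|---|---|---|
| 24 | 100% | 120 | 61/120 = 50.8% |
| 20 | 90% | 90 | 61/90 = 67.8% |
| 18 | 80% | 72 | 61/72 = 84.7% |

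**4. The SAP tables.** Each visit column holds at most 24 pairs, so no column can exceed 60 for either comparator. The protocol criterion cannot be read from these tables without pooling, which the SAP does not specify for it.

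**5. What a small count does to the rule (exact binomial, pairs taken as independent).**

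| Pairs | Needed for 65% | Pass if true share 55% | Pass if true share 60% |
|---|---|---|---|
| 61 | 40 (0.65 × 61 = 39.65) | 6% | 23% |
| 24 | 16 (0.65 × 24 = 15.6) | 17% | 33% |

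Pairs from one eye are correlated. For 13 patients with five visits each, the effective number lies between 13 (every visit in a patient gives the same answer) and 65 (independence). An interval that ignores this will be too narrow.

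**6. What 65% means.** For normal differences with zero bias, 65% within +/-5 mmHg gives SD = 5 / z_0.825 = 5.35 mmHg. The 95% limits of agreement are then +/-1.96 × 5.35 = +/-10.5 mmHg.

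**The case against.** The strongest defence has three parts.

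- **The shortfall is improbable for GAT.** Up to 120 averaged pairs are available. The protocol does not define a pair, so counting readings would raise the number: at two pairs per visit, 7 × 5 × 2 = 70 needs only seven complete patients. This stands in part. It makes a GAT shortfall less of a worry, but it also shows that the trigger depends on a definition the protocol does not give.
- **The study is exploratory.** SAP section 8.1.3 plans no tests. The SAP provides 95% intervals for response rates, the mean and SD of differences, concordance coefficients and Bland-Altman plots, so poor agreement would be visible. This stands. But the protocol still sets a numerical acceptance criterion, and section 7.2 says the study is designed to show agreement.
- **The adjustment is absent from the SAP.** That is true, but so is the criterion, and SAP section 9 does not record its removal.

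A reader might also infer three stronger points that the documents do not support.

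- **That DCT will probably fall short.** DCT availability is not given, and the protocol does not say that the count applies to DCT alone.
- **That the criterion cannot be failed.** Above 60 pairs the 65% is fixed; the opening exists only after a shortfall.
- **That 65% is below the agreement of GAT with itself.** Protocol section 3.3 says "The level of imprecision in repeated IOP measurements has been estimated at +/- 5 mmHg" and that "a difference greater than 7 mmHg must be seen between single pre- and post-treatment IOP levels". Read as 95% limits, these are consistent: 5/1.96 = 2.55, × √2 = 3.61, × 1.96 = 7.07. Two such readings would agree within 5 mmHg about 83% of the time. But the passage does not name GAT, concerns single readings over time, and does not compare two methods. Section 3.3 says GAT error depends on corneal properties. Such error would largely recur in repeat readings of the same eye, but not in a comparison with a sensor. Section 8.2.2 expects differences between the methods. The 83% is therefore not a valid benchmark.

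**Conclusion.** The point holds. Both footnotes direct a change to the primary objective after the pair count is known, with no rule, direction or limit, where the differences can be known too. A shortfall is possible rather than shown to be likely. On the SAP's averaged pair it occurs with 12 or fewer patients. If the count is per comparator, it occurs for DCT with fewer than 61 of at most 120 patient-visits. These figures assume one pair per patient, visit and comparator. The size of any adjustment cannot be derived from the documents, so no lowered bar should be attributed to the sponsor.

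The SAP makes matters worse: it omits the 65% and the pair count, tabulates the split by visit with at most 24 pairs, and does not declare the omission. The documents do not show that 65% is the wrong figure. Its meaning, limits of about +/-10.5 mmHg under normality and zero bias, could usefully be stated. This should be changed, though it does not invalidate the study.

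**What to change.** In the protocol:

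1. Delete the footnote in the Synopsis and its repeat under section 9.1.4.
2. State that 65% within +/-5 mmHg applies unchanged whatever the number of pairs, pooled over V09-V13 and separately for GAT and DCT.
3. Define a pair as the averaged comparator readings and the averaged ARGOS-SC readings of the matching series, for one patient at one visit.
4. State that a comparator with 60 or fewer pairs is reported descriptively only, with its proportion and a 95% confidence interval that allows for repeated visits per patient (for example, by resampling patients).

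In the SAP, carry the same criterion, pair definition and interval into section 8.5, and add a pooled row or column to Tables 2.1.1 and 2.1.2 beside the by-visit results. If the sponsor prefers to drop the criterion, section 9 must say so and why. Optionally, note the +/-10.5 mmHg equivalent and its assumptions beside the 65%.

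The cost is wording and one extra summary per comparator. No data collection changes. The sponsor gives up the option to move the bar and accepts that a comparator with too few pairs yields no pass or fail statement.

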 Implantdata Ophthalmic Products GmbH	Clinical Investigation Plan ARGOS-SC01_Follow-up	Revision C  Page 15 of 97
---	---	---------------------------------

## 2. ABBREVIATIONS AND DEFINITIONS

Abbreviation	Definition
α	Type I error
ADE	Adverse Device Effect
AE	Adverse Event
AS	Anterior Segment
ASADE	Anticipated serious adverse device effect
ASIC	Application specific integrated circuit
BfArM	Bundesinstitut für Arzneimittel und Medizinprodukte
BMO-MRW	Minimum rim width at Bruch membrane opening
CIP	Clinical Investigation Plan
D	Day
dB	Decibel
DCT	Dynamic contour tonometry
EC	Ethics Committee
eCRF	Electronic Case Report Form
EEPROM	Electrically erasable programmable read-only memory
ETDRS	Early Treatment Diabetic Retinopathy Study
EtO	Ethylene oxide
FAS	Full-analysis-set
GAT	Goldmann Applanation Tonometry
GCP	Good Clinical Practice
GDD	Glaucoma Drainage Device
GSM	Global System for Mobile Communications
IB	Investigator's Brochure
ICD	Implantable Cardioverter Defibrillator
ICH	International Conference on Harmonisation
IFU	Instruction for Use
IO	Intraocular
IOL	Intraocular lens
IOP	Intraocular Pressure
ISF	Investigator Site File
ISO	International Organization for Standardization
LAL	Limulus amebocyte lysate
MHz	Megahertz
MEMS	micro-electromechanical system

 Implantata Ophthalmic Products GmbH	Clinical Investigation Plan ARGOS-SC01_Follow-up	Revision C  Page 17 of 97
--	---	---------------------------------

mm	Millimeter
mmHg	millimeter(s) of mercury (a unit of pressure equal to the pressure that can support a column of mercury 1 millimeter high)
MPG	Medizinproduktegesetz
MRI	Magnetic resonance imaging
N	Sample number
NCT	Non-contact tonometry
ND:YAG	Neodymium doped yttrium aluminum garnet
NPGS	Non-penetrating glaucoma surgery
OCT	Optical coherence tomography
OU	Oculus Uterque
P	Pressure or statistical significance
PIC	Patient informed consent
PS	Posterior Segment
RA	Regulatory Authority
Rev.	Revision
RNFL	Retinal Nerve Fiber Layer Thickness
SADE	Serious Adverse Device Effect
SAE	Serious Adverse Event
SAP	Statistical Analysis Plan
SC	Suprachoroidal
SDV	Source Data Verification
T	Tesla
TDM	Trabeculo-descentement's membrane
TMF	Trial Master File
V	Visit
VQoL	Vision-related quality of life
USADE	Unanticipated serious adverse device effect

 Implantata Ophthalmic Products GmbH	Clinical Investigation Plan ARGOS-SC01_Follow-up	Revision C  Page 18 of 97
--	---	---------------------------------

